Although osteonecrosis is considered a significant contributor to the intermediate- and long-term morbidity of ALL therapy, patient perspectives on the impact of osteonecrosis are lacking. We will thus evaluate the impact of therapy and osteonecrosis on the patient experience using the validated patient-reported tool PROMIS tools.³²⁻³⁵ We will further assess the impacts of therapy on patient quality of life with semi-structured interviews.^{36,37}

3.0 RESEARCH PARTICIPANT ELIGIBILITY CRITERIA AND ENROLLMENT

According to institutional and NIH policy, the study will accession research participants regardless of gender and ethnic background. Institutional experience confirms broad representation in this regard.

3.1 Inclusion Criteria

- 3.1.1 Patient is being treated for newly diagnosed acute lymphoblastic leukemia or lymphoma (ALL) on the TOT17 protocol. Patients do not need to be hypertensive to enroll.
- 3.1.2 Patient is 10 years of age or older at the time of enrollment on TOT17.
- 3.1.3 Patient has completed ≤ 4 days of protocol therapy (patients are eligible on Day 4 of TOT17 therapy).

3.2 Exclusion Criteria

- 3.2.1 Moderate-severe renal dysfunction (glomerular filtration rate <45 ml/min/1.73m²).
- 3.2.2 Down's syndrome (germline Trisomy 21) or other syndrome resulting in growth delay or alterations in stature.
- 3.2.3 Chronic inability to ambulate. Patients with limitations in movement due to acute complications of leukemia/lymphoma are not excluded.
- 3.2.4 Permanent contraindication to MRI evaluation.
- 3.2.5 Participants who are pregnant or lactating. Males or females of reproductive potential must agree to use effective contraception for the duration of study participation.

3.2.6 Inability or unwillingness of research participant or legal guardian/representative to give written informed consent.

3.4 Enrollment on Study at St. Jude

A member of the study team will confirm potential participant eligibility and complete all sections of the Participant Eligibility checklist, print, and sign. If the enrollment will be entered by Clinical Trials Operations (CTO), then the study team must send the completed checklist to CTO by email [REDACTED] or fax [REDACTED] [REDACTED] (follow fax by a phone call to [REDACTED] to ensure receipt).

The Study Team or CTO will enter the Eligibility checklist information into the central enrollment system and release an informed consent form. The study team will provide a copy of the study informed consent form (ICF) to the participant family for their consideration and reference. The entire signed ICF must be forwarded to CTO: [REDACTED] or faxed [REDACTED] so that the enrollment will show in the protocol Milli tab and for study-specific orders to be generated in Milli.

To assist with enrollments and consent release, the CTO staff is available during office hours. After hours, weekends, and holiday patient enrollment issues please call the St. Jude study coordinator or refer to the CTO intranet site for additional resources and instructions: [REDACTED].

3.5 Enrollment Instructions for Collaborating Sites

Before the collaborating or enrolling affiliate sites screen or enroll a study participant, the site completes a RIN request form and submits it to CTO by e-mail:

[REDACTED] or fax [REDACTED] (follow fax by a phone call to [REDACTED] to ensure receipt). A RIN is an eight-digit automated number beginning with an "R". Once the form is received, St. Jude will register the research participant and then email the RIN to the email address provided on your registration form. This will register the participant only; it will not enroll the participant on the study. After hours, holidays, and weekends the site RIN request will be answered by the Patient Registration team.

To *enroll* the study participant, after the RIN is obtained, the site study team will complete an eligibility checklist and fax it to [REDACTED] or by email [REDACTED] (follow with a phone call to [REDACTED] to ensure receipt). The CTO will enter the Eligibility Checklist information into the central enrollment system to officially enroll the participant on the trial. Collaborating sites are not required to forward a fully executed (signed) Informed Consent Form to St. Jude.

4.0 TREATMENT PLAN

4.1 Treatment

Following enrollment and randomization, a target systolic blood pressure range will be chosen for each participant based on their randomization arm, age, sex, and height. Target blood pressures for girls randomized to standard and intensive blood pressure control are shown in Tables 1a and 1b, respectively. Target blood pressures for boys randomized to standard and intensive blood pressure control are shown in Tables 2a and 2b, respectively. For patients ages 10-12 years, select the height column closest to their true height. If two columns are equidistant from their true height, select the lower height.

Patient randomization will be stratified based on patient’s location (Memphis vs. other), use of antihypertensives prior to randomization, and factors known to influence osteonecrosis risk, specifically sex and self-declared race (non-Hispanic white vs. other).

Patients will begin antihypertensive therapy to achieve the targeted blood pressure on day 4. Patients already receiving antihypertensive therapy prior to day 4 should have their therapy adjusted according to the guidelines below. **Patients requiring an antihypertensive should be started on lisinopril** (initial dose 2.5mg daily) unless there is a contraindication to its use. Lisinopril dose may be escalated as indicated. Recommended second line agents for use when lisinopril is contraindicated include angiotensin receptor blockers (e.g. losartan 25mg daily), beta-blockers (e.g. carvedilol 3.125mg BID or, if cardiac rate control is required, metoprolol 12.5mg BID) or a calcium channel blocker (e.g. amlodipine 2.5mg daily).

Table 1a: Girls’ Standard Arm Systolic Blood Pressure Targets							
Age/Height (cm)	Height 5%	Height 10%	Height 25%	Height 50%	Height 75%	Height 90%	Height 95%
10 years	130 cm	132 cm	136 cm	141 cm	146 cm	150 cm	153 cm
Standard Low End Target (mmHg)	109	110	111	112	113	115	116
Standard High End Target (mmHg)	113	114	114	116	117	119	120
11 years	136 cm	138 cm	143 cm	148 cm	153 cm	157 cm	160 cm
Standard Low End Target (mmHg)	111	112	113	114	116	118	120
Standard High End Target (mmHg)	115	116	117	118	120	123	124
12 years	143 cm	146 cm	150 cm	155 cm	160 cm	164 cm	166 cm
Standard Low End Target (mmHg)	114	115	116	118	120	122	122
Standard High End Target (mmHg)	118	119	120	122	124	125	126
13+ years	All heights						
Standard Low End Target (mmHg)	130						

Standard High End Target (mmHg)	135						
Table 1b: Girls' Intensive Arm Systolic Blood Pressure Targets							
Age/Height (cm)	Height 5%	Height 10%	Height 25%	Height 50%	Height 75%	Height 90%	Height 95%
10 years	130 cm	132 cm	136 cm	141 cm	146 cm	150 cm	153 cm
Intensive Low End Target (mmHg)	96	97	98	99	101	102	103
Intensive High End Target (mmHg)	103	103	105	106	108	109	110
11 years	136 cm	138 cm	143 cm	148 cm	153 cm	157 cm	160 cm
Intensive Low End Target (mmHg)	98	99	101	102	104	105	106
Intensive High End Target (mmHg)	105	106	107	109	110	112	113
12 years	143 cm	146 cm	150 cm	155 cm	160 cm	164 cm	166 cm
Intensive Low End Target (mmHg)	102	102	104	105	107	108	108
Intensive High End Target (mmHg)	108	109	110	112	113	114	114
13+ years	All heights						
Intensive Low End Target (mmHg)	110						
Intensive High End Target (mmHg)	120						

Table 2a: Boys' Standard Arm Systolic Blood Pressure Targets							
Age/Height (cm)	Height 5%	Height 10%	Height 25%	Height 50%	Height 75%	Height 90%	Height 95%
10 years	130 cm	133 cm	137 cm	141 cm	146 cm	150 cm	153 cm
Standard Low End Target (mmHg)	108	109	111	112	113	115	116
Standard High End Target (mmHg)	112	113	114	116	118	120	121
11 years	135 cm	137 cm	142 cm	146 cm	151 cm	156 cm	159 cm
Standard Low End Target (mmHg)	110	111	112	114	116	117	118
Standard High End Target (mmHg)	114	114	116	118	120	123	124
12 years	140 cm	143 cm	148 cm	153 cm	158 cm	163 cm	166 cm
Standard Low End Target (mmHg)	113	114	115	117	119	121	122
Standard High End Target (mmHg)	116	117	118	121	124	126	128
13+ years	All heights						
Standard Low End Target (mmHg)	130						

Table 2a: Boys' Standard Arm Systolic Blood Pressure Targets							
Age/Height (cm)	Height 5%	Height 10%	Height 25%	Height 50%	Height 75%	Height 90%	Height 95%
Standard High End Target (mmHg)	135						

Table 2b: Boy's Intensive Arm Systolic Blood Pressure Targets							
Age/Height (cm)	Height 5%	Height 10%	Height 25%	Height 50%	Height 75%	Height 90%	Height 95%
10 years	130 cm	133 cm	137 cm	141 cm	146 cm	150 cm	153 cm
Intensive Low End Target (mmHg)	97	98	99	100	101	102	103
Intensive High End Target (mmHg)	104	104	106	107	108	108	109
11 years	135 cm	137 cm	142 cm	146 cm	151 cm	156 cm	159 cm
Intensive Low End Target (mmHg)	99	99	101	102	103	104	106
Intensive High End Target (mmHg)	105	106	107	108	109	111	112
12 years	140 cm	143 cm	148 cm	153 cm	158 cm	163 cm	166 cm
Intensive Low End Target (mmHg)	101	101	102	104	106	108	109
Intensive High End Target (mmHg)	107	108	109	110	112	114	115
13+ years	All heights						
Intensive Low End Target (mmHg)	110						
Intensive High End Target (mmHg)	120						

Patients will begin antihypertensive therapy to achieve the targeted blood pressure on Day 4 of Remission Induction on TOT17. Patients already receiving antihypertensive therapy prior to Day 4 should have their therapy adjusted according to the guidelines below.

During outpatient visits, blood pressures measured should be performed after the patient has been sitting at rest for at least 10 minutes and is not experiencing pain or anxiety.

During induction, blood pressure adjustments will be made for each patient based on the mean blood pressure over the preceding 4 days (minimum 2 measurements) unless indication for immediate change is met (listed below). Blood pressures obtained while a patient is sedated for procedures should not be included in the evaluated blood pressures when determining whether to adjust antihypertensive medications. Patients with mean blood pressures outside of the target range should have antihypertensive therapy adjusted in an attempt to reach the goal range. However, if prior changes to medication have been made within 7 days and blood pressures are both 1) closer to the target range than at the time of prior medication change and 2) within 10mmHg of the goal range following that change, further modifications can be delayed until a subsequent visit.

Immediate changes to antihypertensive therapy are indicated if:

- 1) systolic pressures are more than 15mmHg above the high end target,
- 2) patients are experiencing headache, vision changes, or neurologic symptoms attributable to hypertension,
- 3) the patient has experienced an episode of syncope,
- 4) the patient's systolic pressure is below 90, or
- 5) the patient is experiencing unacceptable toxicity from their current antihypertensive therapy.

Patients will continue antihypertensive therapy (as needed to achieve the targeted blood pressure range) during phases of therapy with scheduled glucocorticoids (i.e. Induction and Continuation, including Reinduction 1 & 2). Patients should continue antihypertensive therapy during other phases if tolerated. Caution is warranted in consolidation (due to the risk of altered renal perfusion or kidney injury) and during immunotherapy (due to the risk of cytokine release induced hypotension).

All antihypertensive agents are FDA approved and commercially available. See package inserts or published references or guidelines for drug information on individual medications.

The completion of Reinduction II dexamethasone marks the completion of the intervention. Following this, physicians should discontinue antihypertensive therapy or continue treatment according to their clinical judgement.

Patients will be evaluated for variations in vascular function due to chemotherapy and the antihypertensive intervention according to the calendar in Table 3 (Section 5.2). Adherence should be verified by the research team utilizing the proportion of days covered at least weekly.³⁸

The term "day" does not refer to an absolute calendar day. It refers to a general 24-hour period. Variations in scheduled evaluations of up to 2 days outside the indicated time points are acceptable if needed for good patients care.

4.2 Participation of St. Jude Affiliates in the Treatment Plan

Patients treated at affiliate sites will participate in the hypertension randomized intervention. They may participate in correlative studies based on the availability of required equipment at each affiliate institution.

4.3 Treatment Modifications for Collaborating Sites

Patients treated at collaborating sites will participate in the hypertension randomized intervention. They may participate in correlative studies based on the availability of required equipment at each collaborating institution. Induction MRI will only be performed for St. Jude patients.

4.4 Supportive Care

Patients should receive supportive care per institutional standard and as directed in the TOT17 protocol.

4.5 Symptom Survey and Semi-structured Interviews

All patients will be asked to complete a symptom survey comprised of the PROMIS Ped 25 profile, PROMIS pain interference 8a, PROMIS physical activity 8a, and PROMIS mobility 8a during induction (day 23-28), during week 17 of continuation (+/- 2 weeks), and continuation week 49 (+/- 3 weeks).

Patients electing to participate in patient interviews about their treatment and symptom burden will be contacted by a study team member. They will be asked to speak about the impact treatment and symptoms have had on their lives. The semi-structured interview will be recorded, with verbal consent at the time of the recording from the patient and, if present, family members confirming the written consent obtained at protocol entry. The semi-structured interview will include the following prompts:

- Tell me about a time when your leukemia treatment changed the way that you did an activity.
 - e.g., Has your leukemia ever made it harder to do something that you wanted to do?
 - Has your leukemia ever prevented you from doing something that you wanted to do?
 - Conversely, has your leukemia ever made it easier to do something that you wanted to do?
- Can you tell me a time when a side effect from treatment impacted your life?
 - e.g., Have you ever felt pain during treatment? If so, tell me about how this affected your ability to live your life.
 - Have you ever experienced nausea or vomiting during treatment? If so, tell me about how this affected your ability to live your life.
 - Are there other symptoms which have affected your ability to live your life?
- What has been the hardest part of treatment for you?
 - What part of treatment has made you feel the most sad?
 - What part of treatment has made you feel the most angry?
 - What part of treatment has made you feel the most frustrated or helpless?
 - As a last resort, if the interviewee is unable to come up with a response despite the question item and the above prompts:
 - Some people tell us that dealing with physical symptoms is the hardest part. Others tell us that feeling anxious or sad is the hardest part. Others say that being away from family/school/friends is the hardest part. And there are so many other things about treatment that are hard. What feels like the hardest part for YOU, personally?

- Tell me about something positive that has happened as a result of your treatment.
 - Has your treatment ever helped you feel better? Tell me about this experience.
 - Has your treatment ever helped you feel relieved? Tell me about this experience.
 - Has your treatment ever helped you feel hopeful? Tell me about this experience.

All interviews will be audio-recorded and transcribed into written narratives for grounded theory qualitative analysis. Patient specific identifiers will be replaced with a code for transcription.

Qualitative analysis of interviews will be performed using the well-described methodology of content analysis.³⁶ Text transcripts will be reviewed in depth by multiple coders to discover similarities and trends related to each interview question item; this process will inform the development of an a priori coding schemata. Through a rigorous, iterative process of memoing and development of codes and code definitions, a preliminary codebook will be created. This codebook will be pilot tested through serial application across pre-selected rich transcripts by multiple coders, with subsequent assessment of inter-rater reliability (goal IRR >0.7). Based on pilot testing feedback, revisions will be made to the codebook to improve content and face validity. Following codebook finalization, codes will be applied across all transcripts by multiple coders working in silos to ensure at least 2 coders per transcript. The unit of analysis will be a segment inclusive of a single sentence or stand-alone phrase. Rigorous reconciliation processes will be conducted to reach consensus, with an objective third-party present to assist with adjudication. Codes will ultimately be organized and collapsed into broader categorized, with the goal of identifying emerging themes upon which to develop concepts and theories.³⁷ As per the inclusion standard in qualitative methodology that investigates descriptive life experiences, if a theme occurs in one interview by one person, it is reported and considered legitimate.³⁶

5.0 REQUIRED EVALUATIONS, TESTS, AND OBSERVATIONS

5.1 Pre-Study Evaluations

All entry/eligibility studies must be performed within 10 days prior to entry onto the trial (unless otherwise specified). Evaluations performed as part of TOT17 evaluation and therapy should be used when feasible to avoid duplicate studies.

Evaluation— must be obtained before enrollment	Within 10 days prior to enrollment
History and physical exam with height (cm), weight (kg), and BSA	X
Diagnosis of acute lymphoblastic leukemia/ lymphoma (ALL)	X
Laboratory studies: CBC with Diff, Chem 18, Urinalysis, PT, PTT	X
Echocardiogram	X
Pregnancy test for females of childbearing potential	X

5.2 Evaluations during Therapy

Evaluation	Timing during Induction	Timing post-Induction
Ambulatory blood pressure monitoring (ABPM)	Once for 12-30 hours on day 4-7, once for 12-30 hours on day 23-28	-
Magnetic resonance imaging of hip and knee	Once during Days 23-28#	Reinduction 2 per Total 17 protocol
Vasomotor testing (arterial elasticity, pulse wave velocity) #	Once during Days 23-28	Once between Early Intensification day 57 and Consolidation day 28, (optional) once Continuation week 120 ±2 weeks
Serum for vascular biomarkers ^{&}	Day 22 +/- 2 days	Week 17 of Continuation (Reinduction II)
Echocardiogram		Once during week 17-19 of Continuation (Reinduction II)#
Symptom survey (PROMIS: Ped 25 Profile, Pain interference 8a, Physical activity 8a, Mobility 8a)	Once on day 23-28	Week 17 of Continuation (Reinduction II) ± 2 weeks, week 49 ± 3 weeks
Semi-structured interview of treatment and symptom burden #		Week 49 ± 3 weeks (with symptom survey)

All days/ weeks refer to the date of Total 17 therapy (i.e. day 22 refers to day 22 of Total 17, not the 22nd day since HYPERION entry or randomization).

***The St. Jude IRB requires that a female patient of childbearing potential must have a negative pregnancy test as a condition of clinical research eligibility.*

SJCRH Memphis patients only

& See HYPERION Manual of Operations for collection, processing and shipping instructions.

Obtain other studies as needed for good patient care and per the TOT17 protocol.

5.3 Response Evaluations

Osteonecrosis will be graded according to CTCAE v4 (to coincide with CTCAE version used in TOT17). Patients will receive MRI screening during Reinduction II as prescribed in the TOT17 protocol. Pain will be ascribed to osteonecrosis or an alternative cause by the treating physician based on clinical history, radiographic findings, and response to therapeutic interventions. MRIs obtained at other times due to clinical concerns/symptoms will be recorded in the research database. MRIs will be evaluated by a pediatric radiologist blinded to the hypertension randomization.

Induction MRIs will only be performed in patients able to complete the study without sedation.

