Brief Outline of Treatment Plan: Patients will be randomized on day 4 of induction therapy to either conventional or intensive blood pressure goals. Patients will be treated with the long-acting antihypertensive lisinopril to achieve blood pressure control as indicated by their randomized arm. Long-acting therapy will be adjusted every 3-4 days as needed to achieve targeted control based on the median of blood pressures obtained in that period. Treatment of hypertension to the target will continue until the completion of reinduction II therapy. Patients will be evaluated for osteonecrosis as indicated in their primary therapeutic protocol using MRI during reinduction II.
Study Design: Randomized unblinded trial of conventional vs. intensive hypertensive control. Evaluation of the MRIs defining the primary endpoint will be performed by a blinded radiologist.
Sample Size: We will randomize 160 evaluable patients (180 total).
Data Management: Data management and statistical analysis will be provided locally by the Comprehensive Cancer Center Hematological Malignancies Program and the Biostatistics Department at St. Jude Children’s Research Hospital.
Human Subjects: The risks to subject will be related to the toxicity of antihypertensive therapy. Side effects are anticipated to be mild and limited to reversible orthostatic/postural hypotension and transient increases in creatinine. Patients will be informed of this and other minor side effects during informed consent discussion. Adverse events will be monitored and reported and treated appropriately.

TABLE OF CONTENTS

1.0	OBJECTIVES	1
1.1	Primary Objective	1
1.2	Secondary Objectives	1
1.3	Exploratory Objectives	1
2.0	BACKGROUND AND RATIONALE	2
2.1	Background	2
2.2	Rationale	2
2.3	Background and Rationale for Ancillary and Exploratory Studies	3
3.0	RESEARCH PARTICIPANT ELIGIBILITY CRITERIA AND ENROLLMENT	4
3.1	Inclusion Criteria	4
3.2	Exclusion Criteria	4
3.3	Research Participant Recruitment and Screening	5
3.4	Enrollment on Study at St. Jude	5
3.5	Enrollment Instructions for Collaborating Sites	5
4.0	TREATMENT PLAN	6
4.1	Treatment	6
4.2	Participation of St. Jude Affiliates in the Treatment Plan	9
4.3	Treatment Modifications for Collaborating Sites	9
4.4	Supportive Care	9
4.5	Symptom Survey and Semi-structured Interviews	10
5.0	REQUIRED EVALUATIONS, TESTS, AND OBSERVATIONS	12
5.1	Pre-Study Evaluations	12
5.2	Evaluations during Therapy	12
5.3	Response Evaluations	13
5.4	Off-Study Evaluations	13

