1.2 Secondary Objectives

- 1.2.1 Evaluate the efficacy of intensive antihypertensive control compared to conventional antihypertensive control in the prevention of clinically significant (CTCAE Grade 2 or higher) and radiologically extensive osteonecrosis, overall and stratified by joints.
- 1.2.2 Compare the frequency of clinically significant and radiographically extensive osteonecrosis in patients receiving antihypertensive therapy and historical controls.
- 1.2.3 Compare blood pressures achieved in intensive and conventional arms using both pressures obtained as part of routine patient care and ambulatory blood pressure monitoring.
- 1.2.4 Compare levels of vascular dysfunction as measured physiologically, radiographically, and in blood samples in patients receiving intensive compared to standard antihypertensive therapy.

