6.0 EVALUATION CRITERIA

6.1 Response Criteria

All patients will be evaluated clinically and radiographically for the development of osteonecrosis. Patients with radiographic (MRI or plain film x-ray) findings of osteonecrosis will be assessed for symptoms by the treating physician or designee. CTCAE version 4 criteria will be used to categorize the severity of osteonecrosis. MRI imaging will be centrally reviewed by a radiologist blinded to treatment assignment to assess the involvement of epiphyseal surfaces (0, <30%, ≥30%) which will be determined for each effected joint.

Blood pressures for each patient will be documented in the research database as the median of each week during induction and the median of each post-induction phase.

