10.5 Secondary Objectives

Evaluate the efficacy of intensive antihypertensive control compared to conventional antihypertensive control in the prevention of clinically significant (CTCAE Grade 2 or higher) and radiologically extensive osteonecrosis, overall and stratified by joints.

A one-sided Chi-square test will be performed on a 2x2 contingency table similar to that in the primary objective, only now the columns are CTCAE Grade 2 ON (No/Yes). This analysis will also be performed for the knees and hips separately. MRI-defined extensive osteonecrosis will also be performed as described above, for knees and hip separately using Chi-square test on contingency tables.

Compare the frequency of clinically and radiographically significant osteonecrosis between patients receiving antihypertensive intervention and historical controls.

The historical control cohort consists of all patients enrolled on TOT-XV and TOT-XVI studies with age at diagnosis 10 years or older. The rate of clinically significant (CTCAE Grade 2+) ON and radiographically significant findings (number of affected joints) will be compared between the intensive BP treatment arm and the historical cohort by Chi-square tests.

Compare blood pressures achieved in intensive and conventional arms using both pressures obtained as part of routine patient care and ambulatory blood pressure monitoring.

The comparison will be done by regression modeling using mixed effect models to account for intra-patient repeated blood pressure measurements. The response variable is blood pressure, the explanatory variables include the BP control arm (intensive vs. conventional), age, sex, race and a random effect with AR(1) working covariance structure.

Compare levels of vascular dysfunction as measured physiologically, radiographically, and in blood samples in patients receiving intensive compared to standard antihypertensive therapy.

The levels of vascular dysfunction are measured by markers such as MRI, eNO synthetase, Von Willebrand Factor, TNF-alpha, D-dimer, PAI-1, E-selectin and ICAM-1; the measurements are all continuous. Each marker will be compared between the intensive BP treatment arm and the standard care arm by Wilcoxon rank-sum test.

Time frame: The analysis will begin within 6 months after the MRI assessments of the last randomized patient is completed.

Responsible investigators: [name], [name]

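### Grade 2+ osteonecrosis rests on an unblinded physician's judgement of what causes pain, is tested one-sided between arms, and has no attribution-free analysis beside it

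*Combined protocol and SAP*

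**What the plan says.** The Protocol Summary describes the study as a "Randomized unblinded trial of conventional vs. intensive hypertensive control", and section 10.2 calls the randomization open label. Under section 4.1, antihypertensive therapy is adjusted to the target range of the assigned arm.

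Blinding is confined to imaging. Section 6.1: "MRI imaging will be centrally reviewed by a radiologist blinded to treatment assignment to assess the involvement of epiphyseal surfaces". The clinical step is not blinded. Section 5.3: "Pain will be ascribed to osteonecrosis or an alternative cause by the treating physician", judged from the history, the imaging and the response to treatment. In section 6.1, patients with MRI or plain-film "findings of osteonecrosis will be assessed for symptoms by the treating physician or designee", and severity is then categorised by CTCAE version 4.

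The outcome enters objective 1.2.1, on efficacy "in the prevention of clinically significant (CTCAE Grade 2 or higher) and radiologically extensive osteonecrosis, overall and stratified by joints", and objective 1.2.2, the historical comparison. For 1.2.1, section 10.5 specifies: "A one-sided Chi-square test will be performed on a 2x2 contingency table similar to that in the primary objective". The columns there are grade 2 osteonecrosis, no or yes. The test is repeated for knees and hips separately. Section 10.5 states no significance level for it.

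For database entry, section 9.1 names protocol-specific data, non-hematologic grade 3-5 adverse events in the glucocorticoid phases, and osteonecrosis of grade 2 or higher.

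**The concern.** Whether a patient counts as a grade 2+ case depends on two clinical judgements: how severe the symptoms are, and whether osteonecrosis causes them. The second leaves much discretion in patients on chemotherapy, who can have pain for many reasons. The person judging is the treating physician or a designee. The protocol does not say that this person is blinded, and treatment to an arm-specific target makes knowledge of the arm likely.

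If pain in the intensive arm is ascribed to another cause somewhat more readily, the recorded rate falls in that arm with no true effect. The one-sided test responds to exactly that shift. What is at stake is the reading of a favourable grade 2+ result. It would naturally be cited as clinical support for the blinded MRI finding, but it would not be independent of knowledge of the arm. The plan blinds the imaging read but leaves the more subjective judgement open.

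**Working it through.** **Inputs**
- 80 evaluable patients per arm (10.1).
- Symptomatic osteonecrosis of about 40% at age 10 or older on the two preceding Total Therapy protocols (2.1). Rates of 30% and 45% are assumed as a range.
- One-sided 5% exact test. The level and the exact form are taken from the primary analysis (10.4), because 10.5 gives neither for this endpoint.
- f, the share of true intensive-arm events ascribed to another cause. This is an assumption; the documents contain no figure.

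**Step 1. Reproduce the plan's own figure.**
Control rate of at least one affected joint: 1 − (0.854 × 70/120 + 0.146 × 0.80) = 1 − (0.4982 + 0.1168) = 0.385. Treatment rate: 0.20. All pairs of outcomes from two Binomial(80) arms were enumerated, rejecting when the one-sided Fisher exact p-value is at most 0.05. The power is 78.7%, as stated in 10.4, so the same test is used below.

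**Step 2. False-positive rate under differential attribution.**
True rate p in both arms. Recorded rates: p in control, p(1 − f) in intensive. Expected number of re-attributed patients: 80 × p × f. At p = 0.40:

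| f | Patients moved | Recorded intensive rate | Exact test | Asymptotic chi-square |
|---|---|---|---|---|
| 0% | 0 | 0.40 | 3.4% | 4.7% |
| 5% | 1.6 | 0.38 | 5.9% | 7.9% |
| 10% | 3.2 | 0.36 | 9.7% | 12.6% |
| 15% | 4.8 | 0.34 | 15.2% | 19.1% |
| 20% | 6.4 | 0.32 | 22.6% | 27.5% |

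**Step 3. Base rate.**
At f = 10%, the exact test gives 8.3% for p = 0.30 and 10.4% for p = 0.45, so the result depends little on the 40%.

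**Step 4. Opposite direction.**
At p = 0.40, if 10% of control-arm events are ascribed elsewhere instead (recorded 0.36 in control, 0.40 in intensive), the exact test gives 1.0%. The error rate then falls, and a true benefit would be harder to show.

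**Step 5. What a few patients can do.**
With 32 control events (40% of 80), the exact test needs 21 or fewer intensive events, a difference of 11. Moving three or four patients does not create significance by itself. It can tip a chance difference over the line.

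**Step 6. What could be checked afterwards.**
- Available: PROMIS pain interference and mobility for all patients at three time points (4.5, 5.2); MRIs done for symptoms, entered in the research database (5.3); blinded involvement per joint (6.1).
- Missing: grade 2 pain ascribed to another cause is not among the events named in 9.1. Sections 6.2 and 8.2 speak more broadly of toxicities and adverse events, but neither asks for the joint.
- PROMIS is not joint-specific, and the patients are unblinded too.

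**The case against.** The strongest reply has four parts.

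- **Attribution is constrained.** Section 5.3 ties it to history, imaging and response to treatment, and 6.1 directs patients with imaging findings to symptom assessment. This stands: it narrows discretion but does not blind it.
- **Size and direction are assumed.** This stands in full. At f = 5% the error rate is 5.9%, close to nominal. At f = 10% about 90% of null trials still show no false benefit. The bias could also run the other way.
- **Some checking is possible.** A reader might infer that differential attribution would leave no trace. The documents do not support that. A patient with a symptom-driven MRI, osteonecrosis on the blinded read and high pain interference, but no grade 2+ event, could be found and counted by arm. The check is only partial, for the reasons in Step 6.
- **The consequence is limited.** The protocol does not rank its secondary endpoints, the primary endpoint is a blinded MRI read, and 1.2.1 itself includes MRI-defined disease. This also stands. It confines the point to how the grade 2+ result may be used.

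It can also be objected that an attribution-free definition is no clean replacement. Severity would still be graded unblinded, scheduled MRI covers only hip and knee (5.2) with one post-induction scan, and unrelated pain would dilute a true effect. That is a good reason to add such an analysis rather than substitute it.

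**Conclusion.** The point holds as a limitation of one secondary endpoint that should be addressed. Cause attribution for grade 2+ osteonecrosis is unblinded, the comparison is one-sided, and neither adjudication nor a sensitivity analysis is planned. Under the stated assumptions (40% true rate in both arms, 80 per arm, exact one-sided 5% level carried over from the primary analysis), re-attribution of 10% of intensive-arm events, about three patients, raises the false-positive rate from 3.4% to 9.7%. Re-attribution of 20% raises it to 22.6%. These are scenarios, not estimates.

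A reader might go further and conclude that a false benefit is likely, or that the trial's main result is compromised. The documents support neither. They give no evidence of the size or direction of any attribution difference, and the primary MRI endpoint is untouched.

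**What to change.** 1. **Sections 5.3 and 9.1:** record joint, CTCAE-equivalent severity and assigned cause for all hip or knee pain of grade 2 or higher, and for other joints when they are imaged.
2. **Section 10.5, objective 1.2.1:** keep the physician-attributed endpoint. Beside it, prespecify an attribution-free analysis that counts grade 2+ symptoms at any joint showing osteonecrosis on the blinded read (Reinduction II or symptom-driven MRI), whatever cause was assigned.
3. **Interpretation:** state that a grade 2+ benefit is taken as independent support for the MRI result only if the two analyses agree.
4. **Objective 1.2.2:** keep the physician-attributed definition for the historical comparison.

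Cost: a few form fields and some wording. The blinded radiologist is already in the plan, so no assessor is added. Some unrelated pain will count in both arms and slightly dilute the effect. Severity grading and the decision to order extra MRIs stay unblinded, and joints without a blinded read are not covered.
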